**2.6.2.2.1 Sensitivity Analysis:**

Four sensitivity analyses are planned for secondary endpoint 2.

- The primary analysis of the LWYY model will be repeated but will also include HF hospitalizations that are adjudicated as Possible HF Hospitalization (i.e. are insufficient data to meet PARAGLIDE-HF criteria) in addition to confirmed HF hospitalizations meeting PARAGLIDE-HF criteria
- The primary analysis of the LWYY model will be repeated but data for CV death, HF hospitalizations and urgent HF visits will be based on investigator reporting and not adjudicated data.
- The primary analysis of the Secondary endpoint 2 will be repeated with Kaplan-Meier estimates for time to the first composite event by the treatment group, in tables and graphs.
- The primary analysis of the LWYY model will be repeated but data that occurs after diagnosis with COVID-19 positive will be censored at the subject level.

**2.6.2.3 Analysis of secondary endpoint 3**

Incidence of a composite endpoint of worsening renal function are defined as:

- renal death (from AE data)
- reaching end-stage renal disease (ESRD) (Sustained eGFR <15mL/min/m^2, chronic dialysis, or renal transplant)
- ≥ 50% decline in estimated glomerular filtration rate (eGFR) relative to baseline [using central laboratory measurements (scheduled or unscheduled visits)]

Among the variables above, none of their components will be adjudicated. The Investigator-reported AE and central laboratory data will be used to identify event of interest in this secondary endpoint 3.

ESRD is defined as one of the following:

- Initiation of dialysis (e.g., hemodialysis, peritoneal dialysis, or continuous eno-venous hemodialysis) after randomization (post-baseline). [from the procedure (PR) data]
- A drop in eGFR from baseline (randomization, i.e. Visit 2) to a value  $<15$  mL/min/1.73m^2 on two consecutive central laboratory measurements [scheduled or unscheduled visits] separated by  $\geq 30$  days. This event will be identified programmatically by the programming team.
- Occurrence of kidney transplantation. [from the procedure (PR) data]

The main analysis of the total number of composite events will be performed using a negative binomial regression model with the count data as the dependent variable. Treatment group and in-hospital/out-of-hospital randomization as fixed-effect factors and log (follow-up duration) as the off-set. The model will be used to estimate event rates and their 95% CIs by treatment group.

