12.5 Analysis of Secondary Endpoints

12.5.1 Secondary endpoints

1. The composite hierarchical outcome consisting of: a) time to CV death, b) number and times of HF hospitalizations during follow-up, c) number and times of urgent HF visits during follow-up, and d) time averaged proportional change in NT-proBNP (from baseline to Weeks 4 and 8)
2. The cumulative number of recurrent composite events overtime, i.e., the total number of composite events of HF hospitalizations, urgent HF visits, and CV death.
3. Incidences of a composite endpoint of worsening renal function defined as:
 - renal death
 - reaching end-stage renal disease (ESRD)
 - $\geq 50\%$ decline in estimated glomerular filtration rate (eGFR) relative to baseline
4. Proportional change in NT-proBNP from Baseline to Week 8
5. Proportional change in hs-Troponin (high sensitivity) from baseline to Weeks 4 and 8
6. Dosing levels and discontinuations
7. Incidence of adverse events of special interest during treatment

- Incidence of symptomatic hypotension
- Incidence of hyperkalemia (potassium >5.5 mEq/L)
- Incidence of angioedema
- Incidence of worsening renal function, defined as an increase in serum creatinine of ≥ 0.5 mg/dl and worsening of the eGFR by at least 25%

Analysis of secondary endpoint 1

This secondary endpoint will be analyzed estimating the unmatched **win ratio** by comparing every participant in the sacubitril/valsartan arm to every participant in the valsartan arm to determine a winner (unmatched pairing method). The estimated win ratio (the total number of wins in the sacubitril/valsartan arm divided by the total number of wins in the valsartan arm) will be calculated. The corresponding null and alternative hypotheses are:

H_{20} : Win ratio is equal to 1, versus

H_{2a} : Win ratio is not equal to 1.

A win ratio greater than 1 will be in favor of sacubitril/valsartan arm. This test will be performed only if the primary null hypothesis (H_{10}) is rejected. The testing of hypothesis H_{20} and calculation of the corresponding two-sided 95% confidence intervals will be performed.

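### SAP 2.6.2.3 gives two conflicting dialysis criteria for ESRD, and the operational one, followed as written, would count temporary dialysis

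*SAP*

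**What the plan says.** Secondary endpoint 3 is a composite of renal death, ESRD and an eGFR decline of at least 50% from baseline. SAP 2.6.2.3 describes ESRD twice.

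- **Component list.** The ESRD bullet carries a parenthesis: sustained eGFR below 15, "chronic dialysis, or renal transplant".
- **Operational list.** A separate list lower in the section opens with "ESRD is defined as one of the following". Its first item is "Initiation of dialysis (e.g., hemodialysis, peritoneal dialysis, or continuous eno-venous hemodialysis) after randomization (post-baseline"), with procedure data as the source. Its second item is a fall in eGFR below 15 "on two consecutive central laboratory measurements [scheduled or unscheduled visits] separated by" at least 30 days. Its third is kidney transplantation.

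On how events are confirmed, the section says: "Among the variables above, none of their components will be adjudicated". On data sources it says: "The Investigator-reported AE and central laboratory data will be used to identify event of interest in this secondary endpoint 3".

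The protocol (section 12.5.1) names the component only as "reaching end-stage renal disease (ESRD") and gives no dialysis criterion.

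**The concern.** The qualifier chronic is in the first list and missing from the second. The second list is introduced as the definition and names its data sources, so it is the one a programmer would most naturally code. One of its examples is continuous veno-venous hemodialysis (misspelt in the SAP). It sets no duration, asks for no continuing need and does not exclude acute kidney injury.

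The trial population makes the case plausible. Patients are enrolled during or within 30 days of a decompensation, and an eGFR as low as 20 is allowed (Protocol 5.1 and 5.2). Protocol Appendix 4 expects potentially reversible renal dysfunction after randomization. SAP 2.3.3 records shock and intensive care around the qualifying event.

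At stake is whether the ESRD component describes lasting kidney failure or a mixture of lasting and temporary dialysis. If two written definitions survive to unblinding, the choice between them could be made with results in view.

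**Working it through.** The plan has no figure to reproduce here. The sample size rests on the primary endpoint alone (Protocol 12.8, SAP 3), and neither document gives an expected renal event rate. The check is therefore a comparison of texts.

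**Step 1. Classify the same patient under each list.**

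| Patient after randomization | Component list | Operational list |
|---|---|---|
| Starts dialysis and stays on it | ESRD | ESRD |
| Dialysed temporarily, then recovers | Not ESRD | ESRD |
| Dies on dialysis soon after starting | Not determined | ESRD |
| One central eGFR below 15, next central value back above 15 | Not ESRD (not sustained) | Not ESRD (two consecutive values needed) |
| Kidney transplant | ESRD | ESRD |

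The lists agree on transplant and on a transient low eGFR. They disagree on temporary dialysis, and only the operational list settles early death on dialysis.

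**Step 2. Look for persistence rules in the composite.**

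- eGFR below 15: two consecutive central values at least 30 days apart.
- Dialysis, operational list: none.
- eGFR decline of 50% or more: none stated; central values from scheduled or unscheduled visits count.

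**Step 3. Look for something that resolves the conflict.**

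- Protocol 10.2.4 and SAP 2.6.1.1 limit adjudication to deaths, hospitalizations and urgent HF visits, and SAP 2.6.2.3 rules it out for this endpoint.
- The protocol does not define ESRD.
- SAP Appendix B, Section 2, repeats the component without a definition. Its model reference is to SAP 2.12, which is not in the public text and so could not be checked.
- The data-source sentence names adverse event and central laboratory data, while the dialysis and transplant items name procedure data.

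**Step 4. Trace where a temporary dialysis episode would enter.**

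- *ESRD as its own component.* Appendix B analyses it separately after pooling with PARAGON-HF, so overlap with other components cannot hide the difference.
- *Main analysis of endpoint 3.* This is a negative binomial model of the total number of composite events. A dialysis start can add to the count even when the patient already has an eGFR event.
- *Incidence and time to first event.* A new event appears only if the patient has not already qualified through the 50% decline.

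**Step 5. Check how far the 50% decline already covers these patients.** The threshold is half the baseline eGFR. For a baseline of 30 it is 30 × 0.5 = 15, so any central value below 15 already qualifies. For a baseline of 20, the lowest eligible value, it is 20 × 0.5 = 10. A fall to 14 is then a decline of (20 − 14)/20 = 30% and does not qualify. Coverage also needs a central sample during the episode. Under Amendment 4, visits after Week 8 fall at Weeks 24, 40, 56, 68 and 84, and unscheduled visits may use a local laboratory (Protocol 8.4.1). Overlap is therefore real but incomplete.

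**The case against.** The strongest reply has four parts.

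1. *The composite already admits transient decline.* The 50% component needs no confirmation, so a reader might wrongly infer that the dialysis wording turns an endpoint of lasting kidney loss into something else. The documents do not support that: the composite is one of worsening renal function, and correcting dialysis alone would not make every component persistent. This part stands, and it confines the clear effect to the ESRD component and the event count.
2. *The SAP states no precedence between the lists.* A reader might infer that temporary dialysis is certain to be counted. It would be if the operational list is coded as written, which is the natural reading, but the text does not say which list governs. The conflict itself stands either way.
3. *The endpoint carries limited weight.* It is one of seven secondary endpoints with nominal p-values and no multiplicity adjustment (SAP 2.6.1). The trial is double-blind and the rule is the same in both arms, so no direction of bias can be inferred. This stands and limits the severity.
4. *The 30-day interval belongs to the eGFR route.* Applying it to dialysis is an extension, and used alone it would drop patients who die on dialysis or reach end of study before day 30. This also stands, and the fix needs a rule for those patients.

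**Conclusion.** The contradiction is in the current SAP text, and nothing in the protocol, the adjudication scope or the visible part of Appendix B resolves it. Followed as written, the operational list would classify temporary dialysis as ESRD, against the SAP's own component wording and unlike the persistence asked of the eGFR route.

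The size cannot be derived. A reader might want to express it as a share of renal events, but the documents supply neither the number of events nor the number of temporary dialysis episodes. For illustration only, suppose 3 to 5 such episodes. Against an assumed 54 events (12% of 450), the share is 3/54 = 5.6% to 5/54 = 9.3%. Against an assumed 30 events, it is 3/30 = 10% to 5/30 = 17%. The answer moves with the assumptions, and none of these inputs except the 450 comes from the plan.

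The effect on the ESRD component and on the total event count is direct. The effect on first-event incidence may be partial. The primary NT-proBNP analysis is unaffected. The conclusion rests on the text alone and on the assumption that some patients receive temporary dialysis.

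**What to change.** Before unblinding, amend SAP 2.6.2.3 as follows.

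- Bring the operational list into line with the component list, so that only chronic dialysis counts as ESRD. One workable criterion is dialysis ongoing for at least 30 days, matching the interval already used for eGFR.
- State how to classify patients who die, or reach end of study, while still on dialysis before 30 days.
- Identify chronic dialysis from the reason, start date and end date that SAP 2.3.4.5 already plans to list for procedures.
- Report temporary dialysis separately.
- Correct the data-source sentence to include procedure data.
- Carry the same definition into Appendix B for the pooled analysis.

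The cost is a short SAP edit and a small programming change using data already planned for listing. The downside is that a few ESRD events may be lost.

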8.3.2 Estimated glomerular filtration rate (eGFR)

The eGFR to determine eligibility of the patient for screening into the trial will be calculated at Visit 1 from the serum creatinine concentration measured at the local laboratory. The eGFR will be further calculated from creatinine concentration measured at Visits 2, 3, 5, 7, 11, 13, 15, and 16 (randomization, Weeks 1, 4, 8, 24, 40, 56, and 68), and end of study (Week 84) at the central laboratory. The eGFR calculation will be based on the Abbreviated Modification of Diet in Renal Disease (MDRD) study equation ([Levey, et al 2007](#)).

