8.4.1 Laboratory evaluations

The local hospital and/or clinic laboratory will be used for all laboratory evaluations required to determine eligibility. If eligibility laboratory assessments were not done during the patient's hospitalization, samples should be collected and sent to the local laboratory. A central laboratory will be used for analysis of all collected specimens from baseline through the final visit. Details on the collections, shipment of samples and reporting of results by the central laboratory will be provided to investigators in the laboratory manual. Results from the local hospital laboratory will be recorded in the eCRF.

Clinically notable laboratory findings are defined in [Appendix 1](#).

Local laboratory assessments may be performed on an as-needed basis for unscheduled visits. Laboratory values that exceed the boundaries of a notable laboratory abnormality must be commented on by the investigator on the source document and additional laboratory evaluations should be performed, as judged appropriate by the investigator. If the laboratory abnormality induces clinical signs or symptoms, or requires therapeutic intervention, then the diagnosis or medical condition must be entered on the patient's AE eCRF. If the laboratory abnormality is the primary reason for an unforeseen hospitalization or otherwise fulfills the seriousness category of an AE, then the procedure for rapid notification of SAEs must be followed. Likewise, if the laboratory abnormality leads to discontinuation from the study drug (temporarily or permanently), the patient must be followed until the abnormality resolves or until it is judged to be permanent. This investigation may include continued monitoring by repeat laboratory testing or by performing additional laboratory tests as deemed necessary by the investigator or the Novartis medical monitor.

Table 8-3 Laboratory Assessments

Test Category	Test Name
Hematology	Hemoglobin, hematocrit, red blood cell count, white blood cell count with differential (Basophils, Eosinophils, Lymphocytes, Monocytes, Neutrophils, Bands, Other (absolute value preferred , %s are acceptable), and platelet count will be measured at Visits 1 (local lab), 2, 7, 11, 13, 15, 16, and 17 (central lab). Hemoglobin A1c will be measured at Visits 2 and 17 (central lab).

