16.4 Appendix 4: Guidelines for the management of renal dysfunction

General principles:

Glomerular filtration rate in HF patients depends on intrinsic renal function and on a balance between afferent and efferent glomerular arterial tonicity. This tonicity is partly regulated by a stimulation of angiotensin II and could be affected by either study medication. Moreover, renal dysfunction may develop or may deteriorate in some patients after study drug administration. These recommendations have been developed to guide the investigators in managing patients with renal dysfunction after randomization.

Two types of response to serum creatinine increase are described:

Surveillance situation

If, at any time after randomization, eGFR decreases by $\geq 25\%$ from baseline (or if serum creatinine concentration increase to 2.5 mg/dL [221 μ mol/L]), the investigator will check for potentially reversible causes of renal dysfunction such as:

- Non-steroidal anti-inflammatory drug intake, antibiotics, or other treatments known to affect creatininemia
- Volume decrease, including that resulting from excessive dosing of diuretics
- Urinary infection
- Urinary tract obstruction
- Study medication

Action situation

If a patient eGFR decreases by $\geq 40\%$ from baseline (or if serum creatinine concentration rises above 3 mg/dL (265 μ mol/L), the investigator will check for potentially reversible causes of renal dysfunction (see above).

If the investigator judges that study medication has to be stopped, he/she will have to contact the Novartis medical monitor or his/her designee. Thereafter, serum creatinine assessments will have to be repeated at least each week until levels return to acceptable values. If study medication was stopped, every effort will be done to restart it again, according to clinical conditions.

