The planned duration of treatment is up to approximately 20 months of double-blind treatment and the last subject randomized will be followed for a minimum of 8 weeks. Subjects may be discontinued from treatment earlier due to adverse event, disease progression and/or if treatment is discontinued at the discretion of the investigator or the subject.

At the randomization visit, all eligible subjects will be randomized via interactive response technology (IRT) to one of the treatment arms. The investigator or his/her delegate will contact the IRT after confirming that the subject fulfills all the inclusion/exclusion criteria. The IRT will assign a randomization number to the subject, which will be used to link the subject to a treatment arm and will specify a unique medication number for the first package of study treatment to be dispensed to the subject.

The randomization numbers will be generated using the following procedure to ensure that treatment assignment is unbiased and concealed from subjects and investigator staff. A subject randomization list will be produced by the IRT provider using a validated system that automates the random assignment of subject numbers to randomization numbers. These randomization numbers are linked to the different treatment arms, which in turn are linked to medication numbers. A separate medication list will be produced by or under the responsibility of Novartis

[figure not shown]
Global Clinical Supply using a validated system that automates the random assignment of medication numbers to bottles containing the study treatment.

There is no planned interim analysis for efficacy in the study. Interim safety assessments are planned to be performed and results will be provided to the Data Monitoring Committee (DMC) for their review and recommendation. The number and/or timing of these safety assessments will be mentioned in the DMC Charter. No adjustment of the level of significance will be made for these interim safety assessments.

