For participants recruited under the Protocol Version 00 (Original Protocol) who do not continue in amendment protocol assessments performed at Weeks 10 or 12 (including, but not limited to, vital signs) are assigned to the open label phase for summarization purposes, unless otherwise noted. Unscheduled assessments are not assigned to a study phase for purposes of by-visit summaries.

For summarization of AEs, notable vital signs and laboratory abnormalities, and symptomatic hypotension by study phase, an assessment during the open label phase is defined as any assessment obtained in the following time interval:

After the date of the Week 8 visit. For participants without a Week 8 visit, a projected Week 8 visit date will be derived relative to their treatment start date.

Participants enrolled under Protocol Version 00 (Original Protocol) who died, withdrew consent, or were lost to follow-up prior to or on their projected Week 8 visit date will be excluded from the open-label phase.

End of Study (EOS)

EOS is obtained directly from the source data. A subject can discontinue treatment (EOT) at any time but continue the study, then the EOS is the study completion date. A subject who completes the study and has an EOS visit. If a subject discontinues the study for any reason, the discontinuation date is the EOS for that subject.

Follow-up for time-to-event analyses

For patients enrolled in the original protocol and continue to an open-label period, events are considered up to the end of their double-blind period (up to Week 8). For patients enrolled in Protocol Amendments 1-4, the events are considered up to their end of double-blind phase (EOS).

In-Hospital / Out-of-Hospital Randomization Status

The status for patient's in-hospital/out-of-hospital randomization is collected as "In-Patient or Out-Patient" category and will be provided by the Interactive Response Technology (IRT).

Year, month and week

For reporting purposes, the rules below will be followed to convert a year, month and week to days.

1 year = 365.25 days

1 month = 30.4375 days

1 week = 7 days

1 day = 24 hours

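### The sustained-eGFR criterion for ESRD requires two consecutive central values at least 30 days apart, so an intervening value that is also low cancels the confirmation

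*SAP*

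**What the plan says.** SAP 2.6.2.3 builds the worsening-renal-function composite from renal death, ESRD and an eGFR decline of at least 50% from baseline. ESRD is reached by starting dialysis, by kidney transplantation, or by a fall in eGFR below 15 mL/min/1.73 m² "on two consecutive central laboratory measurements [scheduled or unscheduled visits] separated by" 30 days or more. No component is adjudicated. Of the laboratory criterion the SAP says: "This event will be identified programmatically by the programming team". The 50% decline also uses central values, but no confirming value is asked for.

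Protocol 8.3.2 sets the central eGFR schedule: "measured at Visits 2, 3, 5, 7, 11, 13, 15, and 16 (randomization, Weeks 1, 4, 8, 24, 40, 56, and 68", and again at end of study. Protocol 8.4.1 states "A central laboratory will be used for analysis of all collected specimens from baseline through the final visit", and also "Local laboratory assessments may be performed on an as-needed basis for unscheduled visits". Protocol Appendix 4 deals with the case where the investigator judges that study medication has to be stopped for renal dysfunction. From then on, "serum creatinine assessments will have to be repeated at least each week until levels return to acceptable values".

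On follow-up, SAP 1.1 says "the last subject randomized will be followed for a minimum of 8 weeks". For original-protocol patients who go on to open label, SAP 2.1.1 says of time-to-event analyses that "events are considered up to the end of their double-blind period (up to Week 8").

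**The concern.** The criterion is labelled as sustained eGFR below 15, but the word consecutive makes it a test of the gap between neighbouring samples, not of how long eGFR stays low. Two values 112 days apart with nothing between them count. Three low values covering 49 days do not, because the middle one splits the interval into two short gaps. More central data therefore make confirmation harder.

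This matters because the event is found by program and nobody adjudicates it, so whatever the sentence says is what will be coded. The criterion is also stricter than its neighbour in the same composite, where one unconfirmed value showing a 50% decline is enough. The SAP does not say which value dates the event, although Cox and Kaplan-Meier analyses of time to first event are planned in 2.6.2.3.1. ESRD is also to be analysed as a separate component in the pooled analysis in SAP Appendix B.

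**Working it through.** The plan gives no figure to reproduce here. The check applies the rule to the sampling schedule.

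**Inputs.** Target days from Protocol Table 8-1: 1, 7, 28, 56, 168, 280, 392, 476, 588. Threshold of 15 and separation of at least 30 days from SAP 2.6.2.3. Lowest eligible eGFR of 20 from Protocol 5.2, exclusion 3.

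**1. Gaps between adjacent scheduled samples** (later day minus earlier day):

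| Pair (days) | Gap | At least 30? |
|---|---|---|
| 1 to 7 | 6 | no |
| 7 to 28 | 21 | no |
| 28 to 56 | 28 | no |
| 56 to 168 | 112 | yes |

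Later gaps are 112, 112, 84 and 112 days.

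**2. Below 15 at Weeks 1, 4 and 8.** Observed span: 56 − 7 = 49 days. The adjacent gaps are 21 and 28, so the rule is not met at target days. If the Week 4 to Week 8 gap widens by 30 − 28 = 2 days, it is met. Otherwise a further low value is needed with no central value in between, either at an end-of-study draw from Day 56 + 30 = 86 or at Week 24 (Day 168). If confirmation only required every central value over at least 30 days to be low, the same patient would be confirmed at Day 56.

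**3. Weekly central retests from a first low value at Day 28.** Every adjacent gap is 7 days.
- Retesting continues throughout: the rule as written is never met through Day 588.
- Retesting runs 16 weeks, to Day 28 + 112 = 140: the next scheduled sample, at Day 168, is only 28 days later, so the rule is first met at Day 280.
- Retesting runs 8 weeks, to Day 84: the rule is met at Day 168, a gap of 84 days.
- Under the span-based reading, confirmation comes at Day 63 in all three cases, since 63 − 28 = 35.

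**4. Who is lost from the whole composite.** A value below 15 is automatically a decline of at least 50% when 0.5 × baseline ≥ 15, that is, when baseline ≥ 30. Below that it need not be:

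| Baseline | Half of baseline | Decline to 14.9 |
|---|---|---|
| 20 | 10 | 25.5% |
| 24 | 12 | 37.9% |
| 28 | 14 | 46.8% |
| 30 | 15 | 50.3% |

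So the patient is lost altogether only if baseline is below 30, eGFR stays between half of baseline and 15, and no dialysis, transplant or renal death occurs.

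**5. Event date.** For a Week 8 and Week 24 pair, dating at the first or at the confirming value differs by 168 − 56 = 112 days.

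**The case against.** The strongest case on the other side is that this is a wording point of limited reach. Much of that stands.

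- **End-of-study draw.** A reader might infer that nobody who misses Week 24 can qualify on scheduled samples, or that Day 168 is the earliest possible completion. The documents do not support either. Protocol 8.3.2 and Table 8-3 include a central sample at the end-of-study visit, and Protocol Section 8 asks for the final-visit assessments when a patient leaves the study early. A low Week 8 value and a low end-of-study value from about Day 86 would qualify.
- **Exact target days.** A reader might also say that no pair through Week 8 can ever qualify. That is true only at target days. Visits are to be held as close to the target as possible, and the SAP 2.4.3 windows allow wide spacing. Counting then depends on a slip of a few days, which is a weakness of the rule but not an impossibility.
- **Earlier amendments.** Counting every visit in Protocol Appendix 5 suggests an unconfirmed run lasting to Week 16. Table 8-3 does not list chemistry at Visit 4 (Week 2) or Visit 10 (Week 16), so that is not established.
- **Retesting.** The weekly creatinine applies only when study drug has to be stopped, not to every patient with renal dysfunction. It breaks a pair only if the samples go to the central laboratory. Local results neither confirm the event nor interrupt it, and Protocol 8.4.1 leaves both routes open.
- **Amendment 1.** It is tempting to say that the exposed patients are exactly those admitted when the eGFR limit was lowered to 20. The protocol does not give the earlier limit.
- **Small consequence.** Patients still low at a later qualifying sample are counted late, not lost. The endpoint is secondary, p-values are nominal, and nothing suggests that the loss differs between arms.

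Requiring 30 days for confirmation is a legitimate choice and is not disputed. The objections limit the reach of the point, but they do not make the written rule measure sustained low eGFR.

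**Conclusion.** The point holds as a defect in an endpoint definition that should be corrected before database lock. As written, an intervening central value below 15 counts against the patient, so 49 days of continuously low scheduled values (Weeks 1, 4 and 8) go unconfirmed at target days, and closer central monitoring delays or prevents confirmation. Patients whose follow-up ends at or near Week 8 are the most exposed, because no later sample can rescue the pair.

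For most others the effect is a late or missing ESRD count. Loss from the whole composite needs all the conditions in step 4. The documents do not give the proportion of patients with baseline eGFR below 30, so the number cannot be estimated; it is probably small.

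The conclusion assumes that consecutive is programmed literally, that visits fall near their target days and, for the retesting part only, that retests are sent to the central laboratory.

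**What to change.** In SAP 2.6.2.3, replace the laboratory criterion with:

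> eGFR <15 at a post-baseline central measurement and at a later central measurement at least 30 days after it, with no intervening central value ≥15; event date = first value <15.

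This keeps the 30-day confirmation, makes intervening low values support the event instead of cancelling it, and settles the event date for the time-to-event analyses.

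The cost is one SAP sentence and a small programming change before database lock, with no new samples. Slightly more events will be counted. One gap remains: a patient first low at Week 4 whose follow-up ends at Week 8 has only 28 days observed and still cannot be confirmed.
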